4. STATISTICAL ANALYSIS POLICY

The purpose of the primary analysis is to evaluate efficacy of TAS-303. To compare the difference between TAS-303 6-mg group and placebo group and between the TAS-303 3 mg group and the placebo group as measured by the percent change in IEF at Week 8 of treatment.

5. TIMING OF STATISTICAL ANALYSIS

Statistical analysis is performed after completion of all patients' study. Before unblinding, preliminary examination (blinded review) of measurement of efficacy and safety, distribution of endpoints, relationship among items, and other aspects will be performed to make decisions regarding handling of patient data, statistical analysis methods, and other points.

6. COMMON ITEMS BETWEEN ENDPOINTS AND STATISTICAL ANALYSES

6.1. Endpoints

The definition of efficacy and safety endpoints are as shown below.

6.1.1. Efficacy Endpoints

6.1.1.1. Evaluation of Symptom Score

Endpoints used to evaluate symptom scores are ICIQ-SF and PGI-I.

6.1.1.1.1. ICIQ-SF

Subjective symptoms (frequency of urine leakage, volume of urine leakage, impact on living, and reason for urine leakage) will be evaluated using ICIQ-SF. The total score of ICIQ-SF is defined as the sum of scores for Q1, Q2, and Q3.

6.1.1.1.2. PGI-I

Patients' impression of improvement of urinary incontinence will be evaluated using PGI-I. Improvement of PGI-I is defined as selection of "Very much better," "Much better," or "A little better."

6.1.1.2. Evaluation of QOL Score

QOL associated with urinary incontinence will be evaluated using I-QOL.

The total score of I-QOL is defined as the sum of scores for all questions. In evaluation of I-QOL scores for individual areas, (1) the score for "avoidance and limiting behavior" is defined as the sum of scores for Questions 1, 2, 3, 4, 10, 11, 13, and 20, (2) the score for "psychosocial impacts" is defined as the sum of scores for Questions 5, 6, 7, 9, 15, 16, 17, 21, and 22, and (3) the score for "social embarrassment" is defined as the sum of scores for Questions 8, 12, 14, 18, and 19.

6.1.1.3. Bladder Diary

Time of voiding, presence or absence of urgency, time of urinary incontinence, reason for leakage, and status of use of pads will be evaluated using Bladder diary.

6.1.1.4. One-Hour Pad Test

Amount of urinary incontinence will be evaluated by a 1-hour pad test.

6.1.2. Safety Endpoints

6.1.2.1. Adverse Events and Adverse Drug Reactions

An AE is any untoward medical condition that have occurred in a patient while participating in this clinical study. Among adverse events, those for which a causal relationship with study drugs is rated as being "reasonably possible" will be considered to be ADRs.

6.1.3. Treatment Compliance Endpoints

6.1.3.1. Compliance Rate

The definition of compliance rate during observation and treatment periods is shown below.

• Observation/Treatment periods discontinued patient

If there is no dose Modification/Interruption/Discontinuation at all, the compliance rate is 100%, and if "Yes" is selected for dose Modification/Interruption/Discontinuation, the following formula shall apply.

[1] Observation period

Observation period compliance rate (%) = $100*[Total\ Treatment\ Days\ (Dose\ Modification/Interruption/Discontinuation\ were not\ included)] / [The larger of 21 and (the last dose date in Observation Period - the first dose date in Observation Period + 1)]$

[2] Treatment period

Treatment period compliance rate (%) = 100*[Total Treatment Days (Dose Modification/Interruption/Discontinuation were not included)] / [The larger of 56 and (the last dose date in Treatment Period - the first dose date in Treatment Period + 1)]

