Urinary flow test			X				X		X
Measurement of residual urine volume by ultrasonography	X 		X				X		X
Concomitant drugs and therapies 									X
Evaluation of adverse events 									X

1. Acquisition of consent: Consent is obtained within 28 days before the enrollment in the observation period.

2. Laboratory test: Hematological tests, serum chemistry and urinalysis are performed.

3. Pregnancy test: Required. When at least 1 year has passed after menopause or when the possibility of pregnancy is medically denied, the test is not necessary. The pregnancy test (serum or urine) before the enrollment must be negative.

4. Concomitant drugs/therapies, evaluation of adverse events: Investigated from the acquisition of consent to the completion of the follow-up observation period.
5. Acceptable range of observation period: Observation period is 3 weeks in principle, but up to 4 weeks is permitted.
6. Acceptable range of timings of visits in treatment period: Week 4 and Week 8 visits  $\pm$  3 days from the scheduled dates are permitted.
7. Follow-up observation: Observation is performed 2 to 4 weeks after the completion of Week 8 of the treatment period. When the treatment is discontinued, it is performed 2 to 4 weeks after the last administration of the study drugs.
8. In cases of discontinuation: Specified observation and tests are performed as much as possible.
9. When the specified observation and tests were performed within 14 days before the enrollment, even if it was before the consent, the results can be used as the data at the time of the enrollment in the observation period.

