3.2. Analysis Populations

The name of analysis populations and their definitions are shown in Table 3-2. The handling of patients with problems in terms of their attribution apart from the criteria shown below will be determined through discussion by the sponsor, the medical experts, and other personnel. The primary efficacy analysis population is PPS while the primary safety analysis population is all treated population.

Table 3-2 Definition of Analysis Populations

Analysis Populations	Definition
All screened population	All patients who gave informed consent
All observation period enrolled population	All patients enrolled in the observation period of this study
All treatment period enrolled population	All patients enrolled in the treatment period of this study
All treated population	Patients in the all observation period enrolled population who have received at least 1 dose of the study drug.
Full Analysis Set(FAS)	Patients in the all treatment period enrolled population who have received at least 1 dose of the study drug for the treatment period and have at least 1 available efficacy endpoint before start of the treatment period and during the treatment period.
	Patients in FAS who have not met any of the following criteria: (1) Patients that have violated any inclusion criteria (2) Patients that have met any exclusion criteria (any criteria that affects the efficacy evaluation)
Per Protocol Set(PPS)	(3) Patients whose compliance rate is < 80% during the treatment period (4) Patients whose rate of completion of Bladder diary (status of urinary incontinence) is < 70% at Week 8 of treatment
	(5) Patients that have received any prohibited concomitant medications or prohibited concomitant therapies that may affect the efficacy evaluation

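### The 56-day floor in the compliance formula can drop a completer with a permitted early Week 8 visit from the PPS although at least 80% of the available doses were taken

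*SAP*

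**What the plan says.** SAP 6.1.3.1 has two branches. First: "If there is no dose Modification/Interruption/Discontinuation at all, the compliance rate is 100" (in %). Second, where a modification, interruption or discontinuation is recorded, the number of treatment days is divided, for the treatment period, by "The larger of 56 and (the last dose date in Treatment Period", less the first dose date in that period, plus 1. For the observation period the denominator begins "The larger of 21 and (the last dose date in Observation Period" and is built the same way. The line above both branches reads "Observation/Treatment periods discontinued patient".

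SAP 3.2 removes from the PPS "Patients whose compliance rate is < 80% during the treatment period" and names the PPS as the primary efficacy population. SAP 7.1 runs the primary test in it.

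The length of each period is not fixed. Under "Acceptable range of timings of visits in treatment period" (Protocol, Table 2 note 6 and Table 5-2 note 6), the Week 4 and Week 8 visits may move by 3 days either way. Note 5 says: "Observation period is 3 weeks in principle, but up to 4 weeks is permitted". Protocol 3.1.1 ends the treatment period at the Week 8 visit, and the visit schedule has remaining drug collected then. Protocol 7.1.1.2 describes the treatment as one dose a day over 8 weeks. Neither document defines the number of days on which a patient was due to dose.

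**The concern.** A compliance rate should compare doses taken with doses the patient could and should have taken. Here the denominator cannot fall below 56, even when the patient attended early within the window and handed back the drug. The days after that visit then count as missed, but only for patients who already have some recorded interruption. A patient with none is given 100% over the same shorter period, so the two branches treat one permitted visit date in two ways.

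What is at stake is membership of the primary efficacy set. Near the 80% cut, a patient can be removed because of the visit date and not because of adherence. The compliance summary in SAP 8.2.2 is also pulled down for every early-visit patient with any missed dose.

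**Working it through.** Neither document works a compliance example, so there is no figure of the plan's to reproduce. The sample-size calculation does not enter.

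**Inputs.** Floor 56 (21 for the observation period) and cut 80%, from SAP 6.1.3.1 and 3.2. Week 8 visit within 3 days of schedule and observation period of 21 to 28 days, from Protocol Table 5-2, notes 5 and 6.

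**Notation.** T = days with drug taken. D = available dosing days. e = doses missed in a run at the end, so the first-to-last-dose span is D − e.

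- SAP score, if any interruption is recorded: 100 × T / max(56, D − e)
- Adherence: 100 × T / D

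**Assumption.** First dose on the enrollment day and none on the visit day, so D runs from 53 to 59. The documents do not state this. Counting the days differently shifts D by a day.

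**Step 1, on-time visit (D = 56).** The span is at most 56, so the denominator is 56 = D. Score and adherence agree wherever the misses fall.

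**Step 2, early visit (D = 53 to 55).** The span is below 56, so the denominator is always 56. The SAP needs T ≥ 0.8 × 56 = 44.8, that is 45. Adherence needs 0.8 × 53 = 42.4, that is 43; 0.8 × 54 = 43.2, that is 44; and 0.8 × 55 = 44.

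| D | T | Missed | T / D | T / 56 |
|---|---|---|---|---|
| 53 | 43 | 10 | 81.1% | 76.8% |
| 53 | 44 | 9 | 83.0% | 78.6% |
| 54 | 44 | 10 | 81.5% | 78.6% |
| 55 | 44 | 11 | 80.0% | 78.6% |

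All four are excluded from the PPS, although at least 80% of available days were taken.

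Away from the cut, with D = 53: no recorded interruption scores 100%. One missed dose scores 52/56 = 92.9%, against 52/53 = 98.1%.

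**Step 3, late visit (D = 57 to 59), if dosing is due up to the visit.** With misses only in mid-period, e = 0, the span equals D, and score and adherence agree. With misses at the end, the span shrinks towards the floor of 56:

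| D | T | Missed | End misses needed to cross 80% | T / D | SAP score |
|---|---|---|---|---|---|
| 57 | 45 | 12 | at least 1 | 78.9% | 80.4% |
| 58 | 45 | 13 | at least 2 | 77.6% | 80.4% |
| 58 | 46 | 12 | at least 1 | 79.3% | 80.7–82.1% |
| 59 | 45 | 14 | at least 3 | 76.3% | 80.4% |
| 59 | 46 | 13 | at least 2 | 78.0% | 80.7–82.1% |
| 59 | 47 | 12 | at least 1 | 79.7% | 81.0–83.9% |

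These patients stay in the PPS with adherence below 80%.

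**Step 4, observation period.** At 21 days, score and adherence agree. At 28 days, if dosing is due throughout, 17 doses and then none scores 17/21 = 81.0% against 17/28 = 60.7%. Stopping after day 21 scores 21/21 = 100% against 21/28 = 75.0%.

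**The case against.** **Only 56 doses are ever due.** Protocol 7.1.1.2 speaks of 8 weeks. On that reading 45 of 56 is 80.4%, the late-visit cases in Step 3 are classified correctly, and 43 or 44 of 56 is rightly below 80%. This stands for Step 3, which is why that part is conditional, and Protocol 7.1.1.1 supports the same reading for the run-in cases in Step 4. It does not rescue the early visit. The treatment period ends at the visit and remaining drug is collected there. The SAP's own 100% branch also treats 53 days without interruption as complete. If 56 doses were due regardless, that patient should score 53/56 = 94.6%. The two branches therefore conflict on either reading.

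**The heading limits the rule to discontinued patients.** It names them, but the 100% branch describes patients with no discontinuation, so the rule must reach completers. If it did not, PPS criterion (3) would have no definition for most patients. The heading is unclear and needs correcting, but it does not settle the matter.

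**A reader might infer that the run-in formula admitted poor compliers to randomization.** The documents do not support this. Protocol 3.2.1 and 4.2.2 leave eligibility to the investigator, and Protocol 5.1.6 has compliance checked at visits from the diary, empty packaging and questioning. The Protocol contains no 21-day formula. The SAP's version 1.0 is dated March 20, 2018, the month in which the study was expected to end. The observation-period rate feeds the compliance summary and reaches the PPS at most indirectly, through PPS criterion (2).

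**The effect is small.** This also stands. In the treatment period only one to three values of T per off-schedule visit day are affected. The FAS analyses in SAP 7.2 and 7.3 have no compliance cut.

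**Conclusion.** The point holds in a limited form. For completers with a permitted early Week 8 visit and some recorded interruption, the 56-day floor counts unavailable days as missed. It excludes from the PPS patients who missed 9 to 11 doses but took 80.0% to 83.0% of the available ones. This rests on the treatment period ending at the visit, and on the day-counting assumption above for the exact values.

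The opposite error, keeping patients with 76.3% to 79.7% adherence, needs three things together: a late visit, doses missed at the end, and dosing due beyond day 56. It would go too far to say that end-of-period misses, or late visits, misclassify patients in themselves. At an on-time visit the floor keeps end misses in the denominator, and at a late visit with only mid-period misses the span equals the available days.

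Few patients should be this close to 80%. The documents give no distribution of adherence or of visit dates, so neither their number nor any effect on the primary result can be computed. This is a minor but definite flaw in a stated rule.

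**What to change.** In SAP 6.1.3.1:

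- Define scheduled dosing days for completers: from the first dose date to the last day on which dosing was scheduled before the visit that ends the period. State whether the visit day counts. Reconcile the definition with Protocol 3.1.1, 7.1.1.1 and 7.1.1.2, so that it is clear whether dosing is due until the visit or for a fixed number of days.
- Use these days as the denominator for every completer, and drop the separate 100% branch.
- Keep the 21/56 floor only for patients who discontinue the period early.
- Correct the heading so that the scope is clear.

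The text change is short and uses dose and visit dates already collected. The downside is that PPS membership may change for a few patients.

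Timing matters. SAP version 2.0 was written before key code breaking, while version 3.0 (September 4, 2018) adds further analyses. If the key code is already broken, keep the existing PPS for the primary analysis, report how many patients would be reclassified in each direction, and run the corrected PPS as a labelled sensitivity analysis recorded in the change log that SAP 10 requires.

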6.2. Common Items in Statistical Analysis

6.2.1. Patient Background

The patient background information investigated at the time of enrollment is listed in Table 6-1. Depending on data of each item, appropriate summaries will be provided by calculation of summary statistics or frequency tabulation. Among patient background information shown in Table 6-1, details of the case where background factor of continuous values are categorized are shown in Table 6-2.

Table 6-1 Background Factors

Item	Factor
Patient Background	Gender, age, height, body weight, presence or absence of medical history, presence or absence of complication, race, ethnic group
Disease Characteristics	BMI, duration of SUI (years), type of urinary incontinence, menopause, delivery, number of deliveries (natural childbirth/caesarean section), menstrual cycle, use incontinence pads, have repair surgery for POP, average number of urinary incontinence episodes per 24 hours, 1-hour pad test

Table 6-2 Detailed Category

Category	Description
Age Category 1	< 65 years, ≥ 65 years
Age Category 2	$<$ 60 years, \ge 60 years
Race	Asian/Oriental, Other
Ethnic group	Japanese, Other
Status of urinary incontinence	Stress Urinary Incontinence, Mixed Urinary Incontinence

6.2.2. Statistical Methods

6.2.2.1. Summary Statistics of Continuous Volume

When summary statistics of continuous volume is provided, it should also show the sample size, minimum, maximum, first quartile, median, third quartile, mean, and standard deviation.

6.2.2.2. Estimation Method

(1) Confidence interval of percentage

The confidence interval of the percentage will be calculated by an accurate method based on F-distribution²⁾

The following formula will be used to estimate the upper limit of confidence interval P_U and lower limit P_L of confidence interval. P indicates the percentage, X indicates the number of patients with events, N indicates the analysis set, and α indicates the two-sided significance level.

$$P = X/N$$

$$P_U = \frac{v_1 F_{v_1, v_2}(\alpha/2)}{v_2 + v_1 F_{v_1, v_2}(\alpha/2)}, \quad v_1 = 2(X+1)$$

$$v_2 = 2(N-X)$$

$$P_L = \frac{v_2}{v_2 + v_1 F_{v_1, v_2}(\alpha/2)}, \quad v_1 = 2(N-X+1)$$

$$v_2 = 2X$$

6.2.3. Allocation Adjustment Factors Used for Analysis

In analyses that use allocation adjustment factors, allocation adjustment factors recorded in CRF will be used for analyses in all treated population/PPS. Analyses in FAS will be performed in two patterns, i.e., a pattern in which allocation adjustment factors recorded in CRF are used and a pattern in which allocation adjustment factors entered in IWRS are used.

6.2.4. Statistical Analysis Software

In this study, all statistical processing will be performed using SAS Version 9.4 and SAS/STAT 14.2.

7. ANALYSES OF PRIMARY ENDPOINT

The below shows the summary of items to be analyzed for the primary endpoint.

7.1. Primary Analysis for Primary Objective

In PPS, the difference between the TAS-303 6 mg group and the placebo group and the difference between the TAS-303 3 mg group and the placebo group will be compared for percent change from the baseline to Week 8 in the average number of urinary incontinence episodes per 24 hours using the student's t-test with the level of significance set at two-sided 5% for the entire test. The significance level for each comparison will be adjusted by Hochberg's method³⁾, considering multiplicity

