#### **Primary Endpoint:**

The following analyses are performed regarding the rate of change in mean number of urinary incontinence per 24 hours at Week 8 of the treatment period from baseline, which is the primary endpoint.

- (1) Main analysis
  - In PPS, the difference between the TAS-303 6 mg group and the placebo group and the difference between the TAS-303 3 mg group and the placebo group are tested by t test using the two-sided significance level of the entire test of 5%. To consider multiplicity, the significance level for each comparison is adjusted by Hochberg's method.
- (2) Sensitivity analysis of main analysis
  - The evaluation in (1) is performed in FAS. Missing values are imputed using last observation carried forward (LOCF).
- (3) Secondary analysis of primary endpoint

The following analyses are performed in FAS and PPS.

  - Summary statistics are calculated for each treatment group. Missing values are not imputed.
  - The rate of change from baseline in mean number of urinary

	
incontinence per 24 hours for each week was analyzed using mixed-effect models for repeated measures (MMRM) to estimate the therapeutic effect of TAS-303 at Week 8 of the treatment period.
 
 
- In PPS and FAS, intergroup comparison is performed by Wilcoxon rank sum test. Missing values are imputed by LOCF.
 
 
(4) Analysis by allocation factor
 
 
- The primary endpoint is analyzed for each condition of urinary incontinence (SUI and mixed urinary incontinence [MUI]).
 
- The primary endpoint is analyzed for each category of mean number of urinary incontinence per 24 hours (less than 2/day and 2 or more/day).
 

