## 3.2 Randomization and Blinding

### 3.2.1 Randomization

This study is a randomized study to be conducted by central enrollment using an interactive web response system (IWRS). Data are entered in accordance with the written procedures for IWRS.

The Investigator or Sub-investigator obtains written consent after providing an explanation to the patients. Patient numbers are 6-digit (eg., 500101). The first digit represents the protocol number (5). The following 3 digits indicate a healthcare facility code. The last 2 digits represent the order of consent at each healthcare facility. These patient numbers are used throughout the entire study. The Investigator or Sub-investigator confirms that the subjects meet the inclusion criteria and do not meet the exclusion criteria for the enrollment in the observation period. Then, the patients concerned are enrolled in the observation period through IWRS. Similarly, for the enrollment in the treatment period, the patients concerned are enrolled in the treatment period through IWRS after the confirmation that they meet the inclusion criteria and do not meet the exclusion criteria for the enrollment in the treatment period. At the time of enrollment in the treatment period, subjects are randomly assigned to 3 mg of TAS-303, 6 mg of TAS-303 or placebo with a ratio of 1:1:1 through IWRS based on the stochastic minimization method.

Patients are stratified using the following allocation adjustment factors.

- Mean number of urinary incontinence per 24 hours at the time of enrollment in the treatment period (less than 2/day and 2 or more/day)
- Condition of urinary incontinence (SUI/MUI)

Through IWRS, a study drug is assigned to each patient, the study site is informed of the drug number assigned to the patient and the instructions regarding the prescription of the study drug are given. For details, see written procedures for IWRS.

If by any chance the study drug different from the drug number assigned by IWRS is dispensed to a patient, the Sponsor must be contacted immediately. The study site must record the cause of the error in prescription or dispensing of the study drug. If administration of the study drug was started in the group different from the assigned one, the administration is continued.

When the “Section 4.3 Patient Discontinuation Criteria” are met, the items related to the discontinuation are promptly entered into IWRS.

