#### **13.1.3.2 Primary Endpoint Analysis**

The following analyses are performed regarding the rate of change in mean number of urinary incontinence per 24 hours at Week 8 of the treatment period from baseline, which is the primary endpoint.

- (1) Main analysis
  - In PPS, the difference between the TAS-303 6 mg group and the placebo group and the difference between the TAS-303 3 mg group and the placebo group are

tested by t test using the two-sided significance level of the entire test of 5%. To consider multiplicity, the significance level for each comparison is adjusted by Hochberg's method.

(2) Sensitivity analysis of main analysis

- The evaluation in (1) is performed in FAS. Missing values are imputed using last observation carried forward (LOCF).

(3) Secondary analysis of primary endpoint

The following analyses are performed in FAS and PPS.

- Summary statistics are calculated for each treatment group. Missing values are not imputed.
- The rate of change from baseline in mean number of urinary incontinence per 24 hours for each week was analyzed using mixed-effect models for repeated measures (MMRM) to estimate the therapeutic effect of TAS-303 at Week 8 of the treatment period.
- In PPS and FAS, intergroup comparison is performed by the Wilcoxon rank sum test. Missing values are imputed by LOCF.

(4) Analysis by allocation factor

- The primary endpoint is analyzed for each condition of urinary incontinence (SUI and MUI).
- The primary endpoint is analyzed for each category of mean number of urinary incontinence per 24 hours (less than 2/day and 2 or more/day).

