2.2.2. Rationale for Sample Size Determination

The number of patients was determined, assuming that efficacy comparable to that of duloxetine can be expected based on results of nonclinical studies. Based on the mean rate of change in the number of urinary incontinence of -62.28% in the duloxetine group and -41.86% in the placebo group from data of a clinical trial of duloxetine, Yentreve clinical study results, Trial ID #6231, the difference between the TAS-303 6-mg or 3 mg group and the placebo group in the rate of change in the number of urinary incontinence, which is the primary endpoint of the present study, was assumed to be -20%. From the standard deviation of 33.73% in the duloxetine group and 32.08% in the placebo group in the above study data, the standard deviation common in two groups was assumed to be 35%. Using the two-sided significance level of the entire test of 5% and the two-sided significance level of each test of 2.5% by Bonferroni's method, when the statistical power is specified as 90% and the rate of withdrawal in the treatment period as about 5%, the number of patients necessary for confirmation of a significant difference between the TAS-303 group and the placebo group is approximately 250 (83 per group).

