7.3. Secondary Analyses of Primary Endpoint

Following analyses will be performed in FAS and PPS:

- Summary statistics will be calculated for each treatment group. Missing values will not be imputed.
- For percent change in the mean IEF per 24 hours from baseline at each week, mixed-effect models for repeated measures (MMRM) will be performed using treatment groups, evaluation time points (Week 4 and Week 8 of treatment), and interactions between the treatment group and the evaluation time point as fixed effects, and allocation factors (status of urinary incontinence [SUI or MUI], mean IEF per 24 hours [≥ 2 per day or < 2 per day]) and age (≥ 60 years or < 60 years) as covariates. Thus, the least mean square (LS Mean) in each treatment group and the difference in the LS mean between each dose group and the placebo group and the two-sided 95% CI will be estimated at Week 8 of treatment. Unstructured covariance structure will be assumed, and toeplitz type will be used in case of no convergence. If convergence is still not achieved, the First-order autoregressive → Compound symmetry → Variance component will be used in this order. The Kenward-Roger method (2009)⁴⁾ will be used to calculate degrees of freedom.
- Intergroup comparison will be conducted using the placebo group as the control by the van Elteren test⁵⁾ using Wilcoxon rank sum test and allocation adjustment factors and age (< 60 years and ≥ 60 years) as strata. If any stratum includes a group with 0 patient, the test will be conducted by excluding age from the strata. The van Elteren

test will be performed in two patterns, i.e., a pattern in which allocation adjustment factors at the time of enrollment are used as strata (analysis in the FAS only) and a pattern in which allocation adjustment factors recorded in CRF are used as strata. Missing data will be imputed using LOCF.

• The time profile of percent change from the baseline will be graphically presented by treatment group.

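### The primary t-test leaves out the two minimisation factors, and age, which the secondary analyses of the same endpoint use; if they are prognostic, a little power is forgone

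*SAP*

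**What the plan says.** - **Primary test.** SAP 7.1 compares 6 mg with placebo and 3 mg with placebo in the PPS, "using the student's t-test with the level of significance set at two-sided 5% for the entire test", and applies Hochberg's method to the two comparisons. Protocol 13.1.3.2 and the synopsis specify the same test. No covariate or stratum enters it, and SAP 11.5 applies multiplicity control to this analysis only.
- **Allocation.** Protocol 3.2.1 assigns patients 1:1:1 "through IWRS based on the stochastic minimization method". The factors are mean incontinence episodes per 24 hours (below 2, or 2 and above) and condition (SUI or MUI).
- **Secondary analyses of the same endpoint.** In SAP 7.3 the MMRM takes both allocation factors "and age (≥ 60 years or < 60 years) as covariates". The rank-based comparison is described as "using Wilcoxon rank sum test and allocation adjustment factors and age" group, the last two serving as strata for the van Elteren test.
- **Source of the factor values.** SAP 6.2.3 states that "allocation adjustment factors recorded in CRF will be used for analyses in all treated population/PPS".
- **Sizing.** SAP 2.2.2 assumes a 20-point difference, SD 35%, 90% power, about 5% withdrawal and "the two-sided significance level of each test of 2.5% by Bonferroni's method", giving about 250 patients (83 per group).
- **Prognosis.** SAP 8.1.10 calls age prognostic after the blinded review. Nothing comparable is said of the two allocation factors, and no R² is given for any of the three. SAP 11.1 assigns covariate adjustment to the MMRM. Neither document explains why the primary test is unadjusted.

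**The concern.** Minimisation keeps the arms close on its two factors, so those factors contribute almost nothing to chance differences between arms. An unadjusted t-test still counts their variation in its error term. If they predict percent change, the estimated standard error exceeds the true one and the test rejects less often than its nominal level allows.

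Age group works differently. It is not minimised, so its chance imbalance and its contribution to the error term match, and the t-test keeps its nominal level. Leaving it out costs power only.

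What is at stake is sensitivity in a dose-exploring phase IIa study. It matters most when one dose works and the other does not, because under Hochberg the working dose is then judged at 2.5%.

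**Working it through.** **1. The plan's sample size.** Inputs from SAP 2.2.2: difference 20, SD 35, two-sided 2.5%, power 90%.

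n per arm = 2 × (z₀.₉₈₇₅ + z₀.₉₀)² × SD² / difference² = 2 × (2.241 + 1.282)² × 1225 / 400 = 76.02, so 77. The noncentral t calculation gives 78.

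Inflating for 5% loss, 77/0.95 rounds up to 82 and 78/0.95 to 83, or 246 to 249 in total. The stated 83 per group is reproduced, and it is the size for the unadjusted test. With 83 × 0.95 = 78.85 evaluable per arm, exact power is 90.3% at 78 and 90.7% at 79. The 90% target is therefore met without covariates.

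**2. One comparison judged at 2.5%.** R² is the assumed share of variance explained by the two minimised factors together. With close balance and 78 per arm:

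- True standard error = 35 × √(1 − R²) × √(2/78).
- The adjusted test uses the critical value 2.264. The t-test's oversized standard error is equivalent to a critical value of 2.264/√(1 − R²).
- Example, R² = 10%: residual SD 33.20, noncentrality 3.762, effective t-test critical value 2.386. Power is 91.4% for the t-test and 93.2% adjusted.

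| Assumed R² | t-test | Adjusted | Gain (points) |
|---|---|---|---|
| 0% | 90.3% | 90.3% | 0 |
| 2% | 90.5% | 90.9% | 0.4 |
| 5% | 90.8% | 91.8% | 0.9 |
| 10% | 91.4% | 93.2% | 1.8 |
| 20% | 92.6% | 95.7% | 3.1 |

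Gains here and below are taken before rounding. Perfect balance is assumed, so these gains are upper limits.

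**3. The full Hochberg procedure, by simulation.** Trials of 249 patients in three arms, minimised on two binary factors, with 5% random dropout and total SD 35. Hochberg rejects both if both p ≤ 0.05, otherwise the smaller if p ≤ 0.025. Assumptions not in the documents: factor prevalences 50% and 35%, equal prognostic strength, an 80% biased coin. There were 200,000 trials per setting (Monte Carlo standard error about 0.05 points). The t-test pools variance over its two arms; the ANCOVA fits three arms plus the two factors.

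| Assumed R² | Family-wise error, t-test | Family-wise error, ANCOVA | Per-dose power, t-test | Per-dose power, ANCOVA | Gain (points) |
|---|---|---|---|---|---|
| 0% | 4.8% | 4.8% | 93.9% | 94.0% | 0.1 |
| 2% | 4.6% | 4.8% | 94.1% | 94.4% | 0.4 |
| 5% | 4.2% | 4.8% | 94.3% | 95.1% | 0.7 |
| 10% | 3.6% | 4.8% | 94.8% | 96.1% | 1.3 |
| 20% | 2.6% | 4.8% | 95.7% | 97.7% | 2.0 |

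Error is with no true effect; power is with both doses at 20 points. The 0.1 at R² = 0 comes from pooling variance over three arms. Power to detect at least one dose rises by 0.0, 0.2, 0.4, 0.7 and 1.0 points.

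Coins of 70% and 90%, and an MUI prevalence of 15% (40,000 trials each), moved the per-dose gains and the t-test error by no more than 0.1 point.

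**4. Age alone prognostic.** Binary age group, assumed 40% prevalence, not minimised. The t-test's family-wise error stays at 4.9%. Per-dose Hochberg power, t-test against a model with both factors and age, is 93.9% against 95.0% at R² = 5%, and 93.9% against 96.0% at 10%.

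**5. Cross-check.** With perfect balance, the true size of one t-test at nominal 5% is 2 × [1 − Φ(1.960/√(1 − R²))]: 4.4%, 3.9% and 2.8% at R² of 5, 10 and 20%. The direction and scale agree with the simulated family-wise error.

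**The case against.** The strongest reply is that nothing is broken. Protocol and SAP agree on the test, it was the basis of the sample size, it meets 90% power, and any error is in the safe direction. This stands, and it limits the point to efficiency.

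Second, the conservatism needs the allocation factors to be prognostic, and the documents never say they are. The endpoint is already expressed relative to baseline, so a split at 2 episodes per day may predict little. This also stands. At R² of 2 to 5% the per-dose gain is only 0.4 to 0.7 points.

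Third, SAP 7.3 already supplies an adjusted Week 8 contrast with a 95% confidence interval in FAS and PPS. A reader will see the adjusted estimate, but not as the test that decides the primary question under Hochberg.

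Fourth, the blinded review changed the secondary covariates and left the primary test alone, which may have been deliberate. No reason is recorded, so this cannot be settled.

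Finally, the chance to change may have passed. Version 2.0 of the SAP is stated to predate key code breaking. Version 3.0 carries no such statement and mostly adds analyses. The documents give no unblinding date, so the recommendation has to be conditional.

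**Conclusion.** The point holds as a minor one. The only multiplicity-controlled test ignores the factors used to allocate patients, and age, while the secondary analyses of the same endpoint use all three. Validity and the planned power are unaffected.

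The size depends on an R² that the documents do not give. Over an assumed 2 to 20% for the two minimised factors, the t-test's family-wise error falls to between 4.6% and 2.6%. Adjustment adds 0.4 to 2.0 points of per-dose power when both doses work, and up to 0.4 to 3.1 points for a dose judged at 2.5%. If only age matters, at an assumed 5 to 10%, the per-dose gain is about 1 to 2 points. If none of the three is prognostic, adjustment gains essentially nothing. Factor prevalences and the coin probability are also assumed, but the results barely changed when the coin and the MUI prevalence were varied.

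**What to change.** **If the key code is unopened:** make the primary test in the PPS either a Week 8 ANCOVA or the Week 8 contrasts of the MMRM already specified in SAP 7.3. Include treatment, both allocation factors (CRF values, as SAP 6.2.3 requires for the PPS) and age group (below 60, 60 and above). Apply Hochberg to the two resulting p-values and keep the t-test as supportive.

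**If the code is already open:** leave the primary test as it is. The adjusted MMRM contrasts are already planned, so no further change follows.

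**Cost:** no new data, and two or three degrees of freedom. The change needs a protocol amendment with investigator agreement and IRB approval (protocol 16.3), and edits to the synopsis, protocol 13.1.3.2, SAP 7.1 and SAP 11.1. The FAS sensitivity analysis in SAP 7.2 would then run with both sources of factor values, CRF and IWRS, under SAP 6.2.3. SAP 10 requires the plan to be final before key code breaking, so that is the deadline.
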